## **12.12            Interim Analysis**

A single interim analysis (IA) is planned to be conducted in the double-blind cohort after approximately 12 subjects per arm have completed 12 weeks of treatment. The final analysis of the double-blind cohort is planned to be conducted after all double-blind subjects have completed Week 16. The IA will include review of all safety and selected efficacy endpoints. The final analysis of the double-blind cohort will review all endpoints (safety, efficacy, and exploratory).

The double blind will be maintained for the IA as the results in the summary listings and tables will be presented only by treatment group. The data will be fully unblinded at the final analysis of the double-blind cohort as the database will include all randomized and completed have undergone a soft-lock at that time.

There will be no formal IAs performed in the open-label single-blind cohort.

A single IA is planned to be conducted in the placebo-controlled 24-week cohort after at least 50% subjects (2:1 randomization) have completed 24 weeks of treatment. The IA will include review of safety and selected efficacy endpoints by treatment group. The IA is being conducted only for internal planning purposes and the study will not be stopped early based on the results of the IA. Therefore, no formal hypothesis testing will occur with no effect on available alpha for the final planned analyses. The final analysis is planned to be conducted

after all subjects have completed Week 30. Results for individual subjects will not be shared with study investigators.

Further details of the IA and final analyses, including statistical considerations and analyses, will be included in the SAP.

## **13            Administrative Aspects**

### **13.1            Protocol Adherence**

The PI must adhere to the protocol as detailed in this document and agree that the Sponsor must approve any changes to the protocol prior to seeking approval from the EC. No alterations in the protocol will occur without agreement between the Sponsor and the PI. No alterations in the protocol affecting patient safety will occur without the express written approvals of the Sponsor, PI, and EC.

### **13.2            Disclosure**

All information provided regarding the study as well as all information collected/documentated during the course of the study will be regarded as confidential. The PI agrees not to disclose such information in any way without prior written permission from the Sponsor.

Any publication of the results either in part or in total (articles in journals or newspapers, oral presentations, abstracts, etc.) by the PI or their representative(s) shall require prior notification and review within a reasonable time frame by the Sponsor and cannot be made in violation of the Sponsor's confidentiality restrictions or to the detriment of the Sponsor's intellectual property rights.

### **13.3            Monitoring**

The Sponsor's or designee's Clinical Research Associate (CRA) will be responsible for monitoring this clinical trial. The CRA will monitor the study conduct, proper CRF and source documentation completion and retention, and accurate study-drug accountability. To this end, the CRA will visit the study site at suitable intervals and be in frequent contact through verbal and written communication. The PI will grant access to all documents (related to the study and the individual subjects) at any time these are requested. In turn, the CRA will adhere to all requirements for patient confidentiality as outlined in the ICF. The PI and PI's staff will be expected to cooperate with the CRA, to be available during a portion of the monitoring visit to answer questions, and to provide any missing information.

### **13.4              Ethics Committee**

This protocol, the informed consent document, and all relevant supporting data must be submitted to the EC for approval. EC approval of the protocol, informed consent document, and any advertisement used to recruit study patients must be obtained before the study may be initiated.

The PI is responsible for keeping the EC advised of the progress of the study and of any changes made to the protocol as deemed appropriate, but in any case, at least once a year. The PI is also responsible for notifying the EC of any reportable AEs that occur during the study.

### **13.5              Informed Consent**

This study will be conducted in compliance with International Conference on Harmonisation (ICH) E6 Good Clinical Practice: Consolidated Guidelines pertaining to informed consent. At the first visit, prior to initiation of any study-related procedures, patients must give their written consent to participate in the study after having been informed about the nature and purpose of the study, participation/termination conditions, and risks and benefits.

The informed consent document must be signed and dated by the patient and PI, or designee, prior to study participation. A copy of the informed consent document must be provided to the patient. Signed consent forms must remain in the patient's study file and be available for verification by Sponsor or its representative at any time.

### **13.6              Records**

The results from Screening and data collected during the study will be recorded in the patient's CRF. To maintain confidentiality, the patients will be identified only by numbers and initials.

The completed CRFs will be transferred to the Sponsor or designee. Copies of each CRF will be retained by the PI. All source documents, records, and reports will be retained by the clinic.

All primary source data or copies thereof (e.g., laboratory records, CRFs, data sheets, correspondence, photographs, and computer records) that are a result of the original observations and activities of the study and are necessary for the reconstruction and evaluation of any study report will be retained in the clinic archives.

Sponsor will inform the PI of the time period for retaining these records to comply with all applicable regulatory requirements. The minimum retention time will meet the strictest (longest) standard applicable to that site for the study, as dictated by any institutional requirements or local laws or regulations, or Sponsor standards/procedures; otherwise, the

retention period will default to the retention period of 15 years following completion of the clinical trial.

### **13.7            Financing and Insurance**

The financing and insurance for this study are outlined in the Clinical Trial Research Agreement.

## 15 Appendices

### Appendix A. NASH Clinical Research Network (CRN) NAFLD Activity Score and Fibrosis Score

Steatosis	S Score	Lobular Inflammation	L Score	Hepatocyte Ballooning	B Score
< 5%	0	None	0	None	0
5%–33%	1	< 2	1	Few ballooned cells	1
34%–66%	2	2–4	2	Many ballooned cells	2
≥ 66%	3	> 4	3	—	—

NAFLD = nonalcoholic fatty liver disease.

Note: NAFLD activity grade score = total score: S + L + B (range 0–8).

Fibrosis Stage	Score
0	No Fibrosis
1a	Zone 3, Mild
1b	Zone 3, Moderate
1c	Periportal Only
2	Zone 3 and Periportal
3	Bridging
4	Cirrhosis

**Appendix B. Food and Drug Administration Toxicity Grading Scale:  
Clinical Abnormalities in Local Injection-Site Symptom Assessments**

Local Reaction to Injection Product	Mild (Grade 1)	Moderate (Grade 2)	Severe (Grade 3)	Potentially Life-Threatening (Grade 4)
Pain	Does not interfere with activity	Repeated use of non-narcotic pain reliever more than 24 hours or interferes with activity	Any use of narcotic pain reliever or prevents daily activity	Emergency room (ER) visit or hospitalization
Tenderness	Mild discomfort to touch	Discomfort with movement	Significant discomfort at rest	ER visit or hospitalization
Erythema/Redness a	2.5–5 cm	5.1–10 cm	> 10 cm	Necrosis or exfoliative dermatitis
Induration/Swelling b	2.5–5 cm and does not interfere with activity	5.1–10 cm or interferes with activity	> 10 cm or prevents daily activity	Necrosis

ER = emergency room.

Note: The FDA Toxicity Grading Scale for Healthy Adult and Adolescent Volunteers enrolled in Preventive Vaccine Clinical Trials can be found at <http://www.fda.gov/BiologicsBloodVaccines/GuidanceComplianceRegulatoryInformation/Guidances/Vaccines/ucm074775.htm>.

a In addition to grading the measured local reaction at the greatest single diameter, the measurements should be recorded as a continuous variable.

b Induration or Swelling should be evaluated and graded using the functional scale as well as the actual measurement.

### **Appendix C. Rosuvastatin Package Insert**

The package insert for rosuvastatin currently being used in the open-label single-blind cohort can be found at the following web link:

[https://www.accessdata.fda.gov/drugsatfda\\_docs/label/2016/079167Orig1s000lbl.pdf](https://www.accessdata.fda.gov/drugsatfda_docs/label/2016/079167Orig1s000lbl.pdf)

The package insert for rosuvastatin currently being used in the placebo-controlled 24-week histology cohort can be found at the following web link:

[http://www.torrentian.com/pisheet/Upload/PI\\_Sheet\\_US/181\\_2.pdf](http://www.torrentian.com/pisheet/Upload/PI_Sheet_US/181_2.pdf)

## **Appendix D. Ezetimibe Package Insert**

The package insert for ezetimibe related to the placebo-controlled 24-week histology cohort can be found at the following web link:

[https://www.accessdata.fda.gov/drugsatfda\\_docs/label/2008/021445s019lbl.pdf](https://www.accessdata.fda.gov/drugsatfda_docs/label/2008/021445s019lbl.pdf)

## Appendix E. Prohibited Hepatotoxic Agents

All other hepatotoxic agents will be left to the discretion of the PI. There should be clear documentation in the patient study records of Investigator approval of use.

Generic Name	Drug Class/Common Use
Acetaminophen > 3000 mg/day	NSAID
Albendazole	Anthelmintics (parasitic infections)
Allopurinol	Antigout
Amiodarone	Antiarrhythmic
Amodiaquine,	Antimalarial
Azathioprine/6-Mercaptopurine	Antineoplastic/Antirheumatic, autoimmune
Buspirone	Sedatives, hypnotics, Psychoactive drug – for anxiety
Busulfan	Antineoplastic/Alkylating, cancer
Carbamazepine	Anticonvulsant
Chemotherapies	
Chlorpromazine	GI, antipsychotic
Dantrolene	Muscle relaxant
Didanosine	Antiviral
Dimethyl Fumarate	For MS
Disulfiram	Alcohol Deterrents
Dronedarone	Antiarrhythmic (AFib/flutter)
Efavirenz	Antiviral
Fenofibrate	Anti-lipemic Hypertriglyceridemia, hypercholesterolemia
Floxuridine	Antineoplastic, cancer
Flutamide	Antineoplastic, nonsteroidal antiandrogen (NSAA)
Glatiramer acetate	For MS
Gold Salts	Antirheumatic, RA
Halothane	Anesthetics for surgery
Hydralazine	Antihypertensive
Infliximab	Antirheumatic, Dermatologic, GI
Interferon alpha	Antiviral
Interferon beta	MS
Isoniazid	Anti TB
Methotrexate	Antineoplastic, Antirheumatic, Dermatologic
Methyldopa	Antihypertensive
Nefazodone,	antidepressant
Nevirapine	Anti-viral (HIV/AIDS therapy)
Nimesulide,	NSAID – COX-2
Norethisterone	For menstrual issues
Phenytoin	anticonvulsant
Pirfenidone	Pulmonary fibrosis
Propylthiouracil	Antithyroid
Pyrazinamide	Anti TB
Quinidine	Antiarrhythmic
Rifampin	Anti TB
Sulfasalazine	Anti-infective (DMARD, anti-inflammatory)
Suramin	Injectable – antiprotozoal agent
Thioguanine	Antineoplastic/Antirheumatic,
Ticlopidine	Antithrombotic, platelet inhibitor
Valproate	Anticonvulsant (epilepsy), mood stabilizer (Bipolar)

1. GLOSSARY OF ABBREVIATIONS

Abbreviation	Description
AE	Adverse Event
ALT	Alanine Aminotransferase
AST	Aspartate Aminotransferase
ATC	Anatomical Therapeutic Chemical
BMI	Body Mass index
C4	7 alpha hydroxy 4 cholesten 3 one
CFB	Change from Baseline
CI	Confidence Interval
CRF	Case Report Form
CRN	Clinical Research Network
CTCAE	Common Terminology Criteria for Adverse Events
ECG	Electrocardiogram
ELF	Enhanced Liver Fibrosis
EOS	End of Study
[REDACTED]	[REDACTED]
GLP-1	Glucagon-like peptide-1
GPP	Good Pharmacoepidemiology Practice
HbA1c	Hemoglobin A1c
HDL-C	High-density Lipoproteins-Cholesterol
HOMA-IR	Homeostasis Model Assessment-estimated Insulin Resistance
[REDACTED]	[REDACTED]
ICH	International Conference on Harmonization
INR	International Normalized Ratio (INR)
LISSAs	Local Injection Site Symptom Assessment
LDL-C	Low-density Lipoproteins-Cholesterol
Max	Maximum
MedDRA	Medical Dictionary for Regulatory Activities

Abbreviation	Description
Min	Minimum
[REDACTED]	[REDACTED]
MRI PDFF	Magnetic Resonance Imaging-proton Density Fat Fraction
N/A	Not Applicable
NA	Not Applicable
NASH	Nonalcoholic Steatohepatitis
PCFB	Percent Change from Baseline
PD	Disease Progression
PK	Pharmacokinetics
PP	Per Protocol
PT	Preferred Term
QC	Quality Control
QTc	Corrected QT Interval
SAE	Serious Adverse Event
SAP	Statistical Analysis Plan
SC	Subcutaneous
SD	Standard Deviation
SE	Standard Error
SOC	System Organ Class
SOP	Standard Operating Procedure
T2D	Type 2 Diabetes
TEAE	Treatment Emergent Adverse Event
TLF	Table, Listing and Figure

2. PURPOSE

The purpose of this statistical analysis plan (SAP) is to ensure that the data listings, summary tables and figures which will be produced, and the statistical methodologies that will be used, are complete and appropriate to allow valid conclusions regarding the study objectives. This SAP only describes the analysis to be conducted on the placebo-controlled 24-week histology cohorts of this trial. The analysis of pharmacokinetics (PK) data will be provided in a separate report and will not be included in this SAP.

The planned analysis for each phase of the study (double-blind, open-label, and placebo-controlled) will be detailed in separate analysis plans.

2.1. RESPONSIBILITIES

██████████ will perform the statistical analyses and are responsible for the production and quality control of all tables, figures and listings.

2.2. TIMINGS OF ANALYSES

An interim analysis is planned to be conducted after approximately 50% subjects per arm have completed 24 weeks of treatment. This will include review of safety and selected efficacy endpoints.

The final analysis of safety and efficacy is planned for all randomized subjects after the last randomized subject has completed the end of study visit at Week 30 or Early Termination visit in the placebo-controlled 24 week histology cohort.

For the purpose of delivery of topline results for the final analysis, a database snapshot will take place before the final database lock. The snapshot will include 24 weeks of selected efficacy and pharmacodynamics (PD) data and 30 weeks of safety data.

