### **12           Data Analysis and Statistical Considerations**

Data analysis will be performed according to the Sponsor's or its representatives' Standard Operating Procedures (SOPs).

Details of statistical parameters and methods to be applied will be provided in a detailed Statistical Analysis Plan (SAP) prior to database lock (unblinding). The general analytical approach for all endpoints will be descriptive in nature.

Unless otherwise stated, the following statistical approaches will be taken:

- Continuous variables: Descriptive statistics will include the number of non-missing values, mean, standard deviation (SD), median, minimum, and maximum. The minimum and maximum values will be presented to the same number of decimal places as recorded in the CRF; mean, median, and SD will be presented to one more decimal place than the raw data.
- Categorical variables: Descriptive statistics will include frequency counts and percentages per category. Percentages will be rounded to one decimal place, with the denominator being the number of subjects in the relevant population.
- Imputation: No missing data will be imputed.
- PK data: Descriptive statistics will include the coefficient of variation. Arithmetic mean and SD will be substituted with geometric mean and SD for all PK-concentration descriptive statistics.
- Confidence intervals (CIs): CIs will be two-sided and will use 95% confidence levels. Any analyses requiring significance testing will use a two-sided test at the 5% significance level.
- Baseline: Baseline will be defined for each patient and will be defined as the last available, valid, non-missing assessment prior to start of first study-drug administration. Unknown, Not Done, Not Applicable, and other classifications of missing data will not be considered when calculating Baseline observations. However, valid categorical observations will be considered for Baseline calculations.
- Analyses: Parametric tests will be used where all statistical requirements are met (e.g., normal distribution). In the event that statistical requirements are not met, non-parametric alternatives will be utilized.

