#### **12.4.5 Per Protocol Population**

The Per Protocol (PP) population will constitute a subset of the Efficacy population and will include subjects that have at least one valid, non-missing post-dose liver fat content measurement. Subjects in the Efficacy population who deviate from the conduct of the study or have an AE deemed by the Medical Monitor to be impactful on the primary endpoint will be excluded from the PP population. This will be the secondary population for the analysis of efficacy and PD endpoints. The PP population will be based on actual treatment received if it differs from that to which the patient was randomized/enrolled.

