5.6. PROTOCOL DEVIATIONS

Subject data will be examined prior to database lock for evidence of protocol deviations in order to identify subjects with major protocol violations which would exclude such subjects from the Per Protocol Population. Possible protocol deviations will be independently reviewed and approved by NGM Biopharmaceuticals Australia Pty Ltd. All protocol deviations will be detailed in a listing by subject and treatment group for the ITT Population. Deviations will be categorized as minor or major based of predefined criteria and assigned by the study team prior to database lock.

Protocol deviations are defined as follows:

- Not meeting all inclusion and exclusion criteria, as detailed in Sections 3.5 of the SAP
- Intake of any prohibited medications, as detailed in Section 6.5 of the protocol
- Failure to follow the conduct of the study

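### SAP 5.6 ties Per Protocol classification to database lock, but topline results come from a snapshot before the final lock, so on the visible text the deadline does not ensure that classification precedes by-arm results

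*SAP*

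**What the plan says.** **Timing of results.** SAP 2.2 states that, to deliver the topline results of the final analysis, "a database snapshot will take place before the final database lock". It adds: "The snapshot will include 24 weeks of selected efficacy and pharmacodynamics (PD) data and 30 weeks of safety data". An interim analysis comes earlier, once about half the subjects have completed 24 weeks. Protocol 12.12 says of it: "The IA will include review of safety and selected efficacy endpoints by treatment group".

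**Timing of classification.** SAP 5.6 says: "Subject data will be examined prior to database lock for evidence of protocol deviations", the purpose being to identify major violators to be left out of the Per Protocol population. It continues: "Deviations will be categorized as minor or major based of predefined criteria and assigned by the study team prior to database lock". It also has possible deviations independently reviewed and approved by a sponsor company. The snapshot is not mentioned.

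**Judgement in exclusions.** Protocol 12.4.5 provides that subjects who depart from study conduct or "have an AE deemed by the Medical Monitor to be impactful on the primary endpoint will be excluded from the PP population". No deadline or blinding condition is attached.

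**Lock and unblinding.** Protocol Section 12 says that a detailed SAP will be provided "prior to database lock (unblinding"); the bracket equates the two events.

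**Use of the population.** The Efficacy population is the main set (Protocol 12.4.4, SAP 5.3). Protocol 12.9.2 repeats the primary analysis on the Per Protocol set, and SAP 8.2 does the same for the secondary efficacy endpoints.

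**The concern.** A pre-lock deadline for deviation review protects a Per Protocol analysis only if nobody can see results by arm before lock. The protocol's bracket suggests that this was the assumption. The SAP then places a topline delivery ahead of the final lock and leaves the deadline in 5.6 where it was. SAP Section 11 records no change from the protocol's planned analysis.

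The value of a Per Protocol repeat is that it shows whether the main finding survives the removal of subjects whose conduct departed from plan. It can do that only if the removals were chosen without knowledge of outcome by arm. If they might not have been, agreement between the two analyses is weak reassurance, and disagreement cannot be interpreted.

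The Liver Histology population may be exposed in the same way. The protocol synopsis gives it the same exclusion by Medical Monitor judgement, and histologic response is the endpoint on which this cohort was sized.

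**Working it through.** **1. Order of events**

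- *Interim (Protocol 12.12, SAP 2.2):* by-arm summaries at about 50% completion.
- *Topline snapshot (SAP 2.2):* 24-week efficacy and 30-week safety data, before the final lock. SAP 6.1 makes tables by treatment group the default, so topline results of a two-arm comparison are naturally read as by-arm results.
- *Deviation review and major/minor assignment (SAP 5.6):* any time up to lock.
- *Final lock.*

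The third step is bounded only by the fourth. Nothing visible places it before the second. Protocol 12.2 says that the sponsor, sites and subjects are blinded, but no visible text says when sponsor blinding ends relative to the snapshot.

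**2. The plan's own sample size, to set the scale**

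Inputs (Protocol 12.1, SAP 3.5): 50% vs 15%, 80% power, alpha 0.05, 2:1 allocation, 15% dropout. The test is two-sided (Protocol Section 12). With pooled variance and no continuity correction, p̄ = (0.15 + 2 × 0.50)/3 = 0.3833, and

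n(placebo) = [1.96 √(0.3833 × 0.6167 × 1.5) + 0.8416 √(0.15 × 0.85 + 0.50 × 0.50/2)]² / 0.35² = 20.6, rounded up to 21.

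That gives 21 + 42 = 63 evaluable, and 63/0.85 = 74.1, rounded up to 75. The stated 50 + 25 is reproduced.

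**3. Illustration of sensitivity**

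The responder counts below are assumed and are not in the documents. The test is the Pearson chi-square of SAP 8.2.6, X² = N(ad − bc)² / (product of the four margins). Every expected count is above 5, so the Fisher rule in 8.2.6 does not apply.

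Borderline start, with exclusions that all favour the drug:

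- 17/42 vs 4/21: X² = 63 × (17 × 17 − 25 × 4)² / (42 × 21 × 21 × 42) = 2.89, p = 0.089.
- Drop two NGM282 non-responders only (17/40 vs 4/21): p = 0.067.
- Drop one placebo responder only (17/42 vs 3/20): p = 0.045.
- Drop all three (17/40 vs 3/20): X² = 60 × (17 × 17 − 23 × 3)² / (40 × 20 × 20 × 40) = 4.54, p = 0.033.

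Start close to the planning assumptions:

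- 21/42 vs 3/21: X² = 63 × (21 × 18 − 21 × 3)² / (42 × 21 × 24 × 39) = 7.57, p = 0.0059.
- Drop two NGM282 responders (19/40 vs 3/21): X² = 6.59, p = 0.010.

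A borderline Per Protocol result can turn on one to three exclusions. In the second example, with an effect near the planned size, two exclusions do not change the conclusion.

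**The case against.** The strongest reply is that the decisive step is inferred. SAP 2.2 gives the purpose and content of the snapshot, not its audience, and no passage says that those who classify deviations will see unblinded output. Protocol 12.2 keeps the sponsor blinded, Protocol 10.5 keeps the investigator and clinic staff blinded until lock, and SAP 2.1 assigns the analyses to a separately named party. The interim is for internal planning, has no formal testing and shares no individual results with investigators. Arm-level summaries do not reveal who is on which arm, whereas the exclusions illustrated above need subject-level allocation. A reader might infer that exclusions will be chosen with results in hand; the documents do not support that.

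SAP 5.4, 5.5 and 10 are blacked out, and a population freeze or access rule would naturally sit there. Its absence cannot be asserted. SAP 5.6 also requires predefined criteria and independent review, which limit discretion even though the criteria are not visible. SAP 2.2 speaks of a final lock and 5.6 of a lock, so the two need not be the same event. Protocol Section 12's bracket concerns when the SAP is due, and Protocol 12.12 links unblinding of the double-blind cohort to a soft-lock.

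All of this narrows the point. What remains is that the visible deadline is tied to an event that follows topline delivery, if the two locks are read as one. That is the natural reading, since SAP 2.2 describes one snapshot and one final lock. Predefined criteria do not settle when, or by whom, they are applied. One listed deviation category, failing to follow study conduct, is open-ended, and the Medical Monitor exclusion is a matter of opinion.

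**Conclusion.** The point holds as a gap in a stated deadline, not as evidence of lost blinding. On the visible text, SAP 5.6 does not ensure that Per Protocol membership is fixed before by-arm results are available. This assumes that its lock is the final lock of SAP 2.2, that topline output is by arm, and that the redacted sections contain no freeze rule.

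The consequence is moderate. A reader might infer that the trial's main conclusion is at risk. It is not, because late Per Protocol changes cannot alter the Efficacy-population analysis. The exposure is confined to the Per Protocol repeats and possibly to the Liver Histology population. The latter is uncertain because Protocol 12.4.6 words its exclusion as one from the Per Protocol set, and SAP 8.2 names the Efficacy population as the main set for secondary endpoints.

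The p-values show only that a borderline result is fragile. They rest on assumed counts with exclusions all in one direction, and they are not an estimate of bias.

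**What to change.** In SAP 5.6, replace the pre-lock deadline, for both the deviation review and the major/minor assignment, with: *before the topline snapshot is unblinded, by staff without access to treatment assignment or to interim results by arm*. Apply the same condition to the Medical Monitor's adverse-event exclusions and to the Liver Histology population. Archive the dated population list. Log any later change with its reason, and show results with and without it. If a redacted section already contains such a rule, 5.6 should refer to it.

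Fixing membership before the interim is not needed, since subjects in it may still have Week 30 data to come. Keeping the classifiers away from by-arm interim results is enough.

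The cost is a short edit to one SAP section and an earlier deviation review meeting. No endpoint, sample size or study procedure changes.
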